ClinicalTrials.gov Data Entry Cover Sheet

Today's date: May 15, 2024 **Document date:** November 15, 2023

Protocol ID: 21287 Clinical Trials.gov ID: NCT05129501

Project Title: The Impact of an Adapted Version of the Strengthening Families Program on IPV

Among Caregivers and ACEs Among Children

Principal Investigator: [name], University of Nebraska-Lincoln

Recruitment and Retention Plan

Careful efforts will be made to **maximize participant enrollment** and **minimize attrition** in the survey and programming portions of the project. As described in the Statistical Design and Power Analysis section of this proposal (referenced in C.14 of the Research Strategy), we will enroll a total of 320 families (160 per condition). Based on previous similar research, including the Pl's work, we anticipate that we will retain 75% of the sample at the 8-month follow-up for a final sample size of 120 families per condition (160 youth and 160 caregivers per condition x 2 conditions for a grand N = 640 youth and caregivers across conditions at the pretest, and 480 across conditions at the 8-month follow-up).

Recruitment

We will recruit from multiple agencies/organizations/schools in Rapid City, including Youth and Family Services; Children's Home Society; Department of Social Services; Rural America Initiative; Rapid City Area Schools: Working Against Violence, Inc.; Girls, Inc.; Rapid City Police Department; Pennington County Sheriff's Office; and Ellsworth Air Force Base. (See enclosed letters of support from these partners.) These partnering agencies/organizations/schools will do the following as detailed in their letters of support: (1) post project information on their social media sites; (2) allow the project team to have a table at events hosted by the school/agency/organization; (3) send recruitment letters to families that are involved with or attend the school/agency/organization; (4) share information about the project with staff so that they can pass along information to the youth and families they serve; and/or (5) encourage families to personally invite other families to the project. We will follow the recommendations for recruitment suggested by the lowa State University Extension (e.g., use positive language when describing the project, personalize invitations). In addition to these efforts we will also "boost" posts on social media to advertise the project, place an advertisement in the local newspaper with project information, saturate the community with fliers advertising the project, and attend numerous community events (e.g., Black Hills Pow Wow, Lakota Nation Invitational, Black Hills Pride). [name] (PI) has used these recruitment methods in another federally funded study (5U01CE003168) in South Dakota (SD) with success (as evidenced by over 80% returned consent forms in schools, for example). Also, as part of this same study, [name] (PI) was able to recruit more than 50 adults (e.g., caregivers, teachers) to participate in interviews and/or focus groups within a 2-week period. We will also advertise the study in other ways as recommended by the Research and Practice Advisory Board (RPAB). In addition, we will offer informational sessions that incorporate culturally grounded "feeds" (dinners to be covered by [name] discretionary funds), which our previous work suggests increases community buy-in and enrollment. Finally, like previous studies in SD, we will engage in "door knocking" on the north side of Rapid City where the vast majority of residents are low income and/or American Indian. Door-knocking includes identifying areas within a community that have a large proportion of the target population. Once identified, members who live within the targeted neighborhoods are recruited and trained to go door to door and explain the nature of the study to potential participants, assess eligibility, and enroll families that are interested and meet inclusion criteria. We have had great success using this method in previous studies, especially with American Indian communities.

Participants will have multiple ways to **enroll** in the study. They will have the option of attending informational sessions in addition to enrolling by phone, email, an online portal on a project website, or in person at various locations across Rapid City (i.e., we will have a strong presence at community events, especially those targeting American Indians and/or low-income individuals). We will also offer to go to the homes of interested participants to enroll them in the study. Interested families will first be asked if they have at least one child between the ages of 10 and 14. Families will also be required to answer "YES" to one or more of the following questions: (1) Is your child American Indian/Alaska Native/Lakota?; (2) Does your family (including all people who work and contribute to the finances of the household) make less than \$25,750 a year (for family of four)? Additionally, at least one caregiver and one child must commit to both the research and programming components of the project to be eligible to participate.

Retention

Intense efforts will be made to **retain** participants. First, at all programming sessions, a culturally tailored meal (e.g., buffalo, fry bread) will be served (paid for by the PI's discretionary funds). Second, we will provide

families with a gift card for each session that they attend (a gift card will be given to each family member who attends). We will also call, text, and email participants of upcoming programming and survey sessions and include reminders on our project social media sites. At the baseline survey, we will collect detailed contact information as well as social media account information. We will use this information to directly contact participants who do not show for a program and/or survey session and are not responsive to our initial contact attempts. We will engage in monthly check-ins with participants in order to keep them engaged and more likely to complete follow-up surveys. During these check-ins we will determine if any contact information has changed. We will also maintain relationships with families by sending them branded goods (e.g., a University of Nebraska-Lincoln T-shirt for the child) and by sending birthday cards. We will also seek participants' approval to locate them via Intelius in the event we are not able to locate them using the contact information provided. Intelius is a database that allows the user to enter an individual's name and/or contact information to receive updates about new contact information (e.g., new address). We have used this in a previous, federally funded study (grant number 2016-SI-AX-0003) with women who have histories of criminal offending, victimization, and addiction to retain over 85% of the sample, and there have been no negative impacts of using this service on participants. Also, widespread community support for this project will likely help with retention. Finally, we recognize the transient nature of the American Indian population in Rapid City, SD. More specifically, some American Indian families in Rapid City, SD, spend some of their time on one of the nearby reservations. We will work with families to enroll them in the study when they anticipate being in Rapid City for the duration of the project. We will also provide options for families to complete the follow-up surveys remotely in addition to having research staff make occasional visits to the nearby reservations for follow-up survey procedures.

## **Statistical Design**

## Data Analysis (Survey Data) Preliminary Analyses.

*Baseline equivalence.* To check the efficacy of the randomization procedures with the goal of creating equivalent groups, we will examine baseline equivalence on demographic characteristics and for each outcome domain between the experimental conditions using multivariate analysis of variance (MANOVA). This will be completed for each analytic sample. Differences less than or equal to 0.05 standard deviations (SD) will be the criterion for satisfying the baseline equivalence requirement. We will account for any differences (> 0.05 SD in absolute value) between groups by including baseline measures (covariates) that require statistical adjustment in analyses of covariance or regression approaches.

*Nesting.* We will also examine the role of nesting within the treatment group, as individuals will be randomized to groups of families who will receive the intervention together (i.e., calculation of intraclass correlations [ICC] based on group assignment and facilitator in relation to outcomes). If needed, the role of group clustering will be accounted for in all analyses.

*Differential attrition.* We will guard against differential attrition by experimental condition. We will track and examine if attrition rates differ for the experimental groups. We expect similar rates of attrition across experimental groups. Furthermore, we will use an intentto-treat (ITT) analytic approach (i.e., use data from all cases of our randomized sample, who will all have baseline data based on our design) in our analyses to limit the bias introduced by missing data. We will conduct Little's MCAR test and Simonoff's regression diagnostic procedures to determine whether overall participant non-response meets the MAR assumptions required by the proposed analytic framework. Missing data assumed to be at least MAR will be dealt with as a function of the data analytic process through maximum likelihood estimation (ML), which makes use of all available data and does not require deletion of incomplete cases.

*Psychometric analyses.* For measures that have been used previously, scale reliabilities will be evaluated for comparability with prior literature using Cronbach's alpha coefficients based on pre-test data. For measures that have not previously been used with this population, psychometric work will be conducted. Confirmatory factor analysis (CFA) will be used to evaluate the hypothesized factor structure using pre-test data. The first stage of the analysis will fit factor models to evaluate the factor structure as compared to theory. To estimate the CFA, we will use the common factor model and full information maximum likelihood-robust (FIML-R) estimation within a structural equation modeling (SEM) framework using Mplus. To determine the best fitting factor model, we will evaluate the fit of the model using multiple indices (i.e.,  $\chi^2$  test statistics, RMSEA < .08; SRMR < .08; CFI > .96174). Based on the psychometric work, adjustments to the measures will be made as necessary. Lastly, we will examine internal consistency estimates of Cronbach's reliability of these measures, when applicable.

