## Outcome Analyses.

*Aim 2c.* The effects of Was'ake Tiwahe program (intervention condition) on youth, caregiver, and family intermediary, primary, and secondary outcomes will be assessed using an intent-to-treat approach (i.e., all participants randomized will be included in analysis) within the

ANCOVA framework. The effects of interest are differences between experimental conditions at post-test and follow-up on youth, parent, and family outcomes, as detailed in the logic model (Research Strategy, Figure 1). These effects indicate whether the outcomes in the intervention condition differ significantly from those in the wait-list control condition. The experimental condition is the independent variable in these models. We will include pertinent covariates (e.g., pre-test measurement of outcome of interest, cohort, youth gender) in all models. At pre-test, we expect that the mean difference between the experimental conditions will not differ significantly from zero, reflecting effective randomization. At post-test and follow-up, we expect the difference between the experimental conditions to be significantly greater than zero, reflecting better outcomes after the intervention period for those in the Was'ake Tiwahe program condition. If nesting is of concern based on preliminary ICC analyses, we will implement the outcome analysis using the ANCOVA framework within a mixed model with random effects for both conditions. We will evaluate our hypotheses by examining significance (p), confidence intervals, and the standardized difference between groups (d).

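### The 0.05 SD baseline limit is only 0.45 standard errors at 160 per arm, so about two thirds of baseline variables will exceed it even when randomization has worked

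*SAP*

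**What the plan says.** In the SAP, Preliminary Analyses, the Baseline equivalence paragraph gives the purpose of the check: "To check the efficacy of the randomization procedures with the goal of creating equivalent groups". It covers demographic characteristics and every outcome domain, and names MANOVA as the method. The criterion is: "Differences less than or equal to 0.05 standard deviations (SD) will be the criterion for satisfying the baseline equivalence requirement". The consequence of exceeding it is: "We will account for any differences (> 0.05 SD in absolute value) between groups by including baseline measures (covariates) that require statistical adjustment". On scope it adds: "This will be completed for each analytic sample".

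The Differential attrition paragraph describes the intent-to-treat approach: "use data from all cases of our randomized sample, who will all have baseline data based on our design".

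Under Outcome Analyses, Aim 2c, the SAP describes baseline balance in other terms: "we expect that the mean difference between the experimental conditions will not differ significantly from zero, reflecting effective randomization". On covariates it says: "We will include pertinent covariates (e.g., pre-test measurement of outcome of interest, cohort, youth gender) in all models". The named covariates are examples, not a closed list.

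The protocol's Recruitment and Retention Plan gives 160 families per condition, hence 160 youth and 160 caregivers per condition at pretest. It expects 75% retention at 8 months.

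**The concern.** A limit used to judge randomization should be exceeded rarely when randomization is sound. If it lies well inside sampling error, exceeding it says almost nothing about the allocation, and a reader of the results could doubt a good randomization.

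The SAP names a MANOVA for the same check without saying how its result relates to the 0.05 SD limit. Aim 2c uses a third yardstick, a non-significant pre-test difference. If these give different answers, the SAP does not say which one counts.

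The limit also affects the outcome models. For an outcome's own pre-test value the trigger changes nothing, because Aim 2c already adjusts for it. For other demographics and outcome domains, a measure enters because it happened to differ between arms, whether or not it predicts the outcome. Since the check is repeated in each analytic sample, post-test and follow-up models could also carry different covariates.

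**Working it through.** **Inputs.** Limit 0.05 SD (SAP, Baseline equivalence). 160 youth and 160 caregivers per arm, 75% retention (protocol, Recruitment and Retention Plan). Baseline data on all randomized cases (SAP, Differential attrition).

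**The plan's own figure.** 160 × 0.75 = 120 families per arm and 640 × 0.75 = 480 people. Both reproduce.

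**Limit in standard errors.** With equal arms, the SE of a standardized mean difference is √(2/n), with n per arm. Under perfect randomization the chance of exceeding the limit is 2 × [1 − Φ(0.05/SE)].

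| Reading of the sample | n per arm | SE | 0.05/SE | Chance of exceeding |
|---|---|---|---|---|
| One respondent type, all randomized | 160 | 0.1118 | 0.447 | 65.5% |
| One respondent type, 8-month completers | 120 | 0.1291 | 0.387 | 69.9% |
| Youth and caregivers pooled as independent | 320 | 0.0791 | 0.632 | 52.7% |

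Simulation with 100,000 draws gave 65.7% at 160 and 69.8% at 120. In the pooled reading the limit is above half a standard error, but over half of variables still exceed it. As a concrete case, for a binary characteristic held by half the sample, 0.05 SD is 0.05 × 0.5 = 0.025, or 0.025 × 160 = 4 families per arm.

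**Sample size at which the limit would suit.** For 95% of variables to fall within 0.05 SD, n = 2 × (1.96/0.05)² ≈ 3,073 per arm.

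**What exceeding the limit tells us.** However badly randomization failed, the chance that a variable exceeds the limit cannot be above 1. The likelihood ratio for failed against sound randomization is therefore at most 1/0.655 = 1.53 for one variable. A variable within the limit is more informative, but all of them falling within it is rare: 0.5–1.4% of perfectly randomized trials with 5 variables, and at most about 0.04% with 10 or 20 (assumed correlation 0–0.6).

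**Beside the MANOVA.** Simulated at 160 per arm under perfect randomization, with 5, 10 or 20 variables correlated 0, 0.3 or 0.6 (assumed; 40,000 trials per cell):
- MANOVA significant: 5.0–5.3%.
- MANOVA non-significant with at least one variable above 0.05 SD: 93.5–95.0%.
- MANOVA non-significant with at least half the variables above 0.05 SD: 67–90%.

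**Effect on the treatment comparison.** All inputs here are assumed: 5 or 15 candidate covariates, equally prognostic, correlated 0 or 0.3, explaining 5–30% of outcome variance beyond the pre-test; the pre-test is always adjusted for, with correlation r to the outcome. There were 10,000 trials per cell, and the comparator fixes the same covariates in advance.
- 160 per arm, r = 0.5: Type I error 2.9–5.3% under the rule. At d = 0.3, power is −0.1 to 1.8 points lower than with all fixed.
- 120 per arm, same r and d: 0.1 to 3.5 points lower.
- 160 per arm, r from 0.3 to 0.7 and d from 0.2 to 0.4: the largest loss is 1.2, 3.8 and 7.6 points when covariates explain 5%, 15% and 30% of variance. The largest losses occur at d = 0.2; at d = 0.4 the loss is at most 0.4 points.

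**The case against.** The strongest objection is that the rule does almost no harm. It uses baseline data only, adjustment for baseline covariates does not bias a randomized comparison, and the power loss is small in the central case. Every input to that loss is assumed. This stands, and it limits the point to reporting and efficiency.

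The rule may also be less mechanical than it looks. The phrase about measures that need adjustment can be read as leaving a judgement step, and the open list under Aim 2c can already hold prognostic measures. If that list is rich, the trigger adds little. This stands too: the criticism of covariate selection applies only beyond what Aim 2c already includes.

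The criterion may come from an external standard, and a closed covariate list may exist elsewhere. The text available names no source for the limit, part of the SAP was not available, and the Research Strategy cited in both documents is not supplied. Neither possibility changes the 65.5%.

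In a sample reduced by attrition, a baseline difference may be systematic, and the trigger would then prompt adjustment. That is a reason to keep the rule as a sensitivity analysis. At 120 per arm, 0.05 SD is still only 0.39 SE.

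Three stronger readings are tempting. A reader might infer that the SAP contradicts itself. It does not: the 0.05 SD limit, the MANOVA and the expectation under Aim 2c are unreconciled standards, and the last is worded as an expectation, not a rule. A reader might infer that the team can pick covariates after seeing outcome results; a trigger based on baseline data gives no such freedom. A reader might infer a biased estimate or an inflated error rate; the calculations show neither.

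**Conclusion.** The concern holds in a limited form. At the planned size, 0.05 SD is 0.45 standard errors, and about two thirds of baseline variables will exceed it when randomization has worked. The 65.5% rests only on the documents' sample size, equal arms and one respondent type per measure. The limit cannot do the job the SAP gives it, and its result will usually sit beside a non-significant MANOVA with nothing in the SAP to reconcile the two.

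For the treatment comparison the consequence is modest: a nominal to conservative test and, at r = 0.5, d = 0.3 and 160 per arm, about 0 to 2 points of power lost. The loss is larger only for small effects with strongly prognostic covariates. These sizes depend on the assumed number, correlation and strength of covariates, none of which the documents give. The SAP should be changed on this point, but the validity of the trial does not depend on it.

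**What to change.** 1. Stop using 0.05 SD as the criterion for randomization and as the covariate trigger for the primary models.
2. Report standardized differences descriptively for each analytic sample. Keep a 0.05 SD table, or a sensitivity analysis adjusted by that rule, if an external standard requires it or if attrition may have caused systematic imbalance.
3. Give the baseline comparison one role, stated consistently under Baseline equivalence and Aim 2c, and say what the MANOVA result is used for.
4. Before outcomes are analysed by arm, fix a closed covariate set for each outcome: pre-test value, cohort, youth gender and the collected baseline measures judged prognostic. Use it whatever imbalance is observed.

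The cost is SAP wording and a few degrees of freedom. The risk is a list cut too short. In one assumed case (160 per arm, 15 independent, equally prognostic covariates explaining 30% of variance, r = 0.5, d = 0.3), the pre-test plus only 4 covariates gave 89.9% power, against 95.3% under the current rule and 97.1% with all 15 fixed. The list should therefore be full.

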## Outcome Analyses.

*Aim 2c.* The effects of Was'ake Tiwahe program (intervention condition) on youth, caregiver, and family intermediary, primary, and secondary outcomes will be assessed using an intent-to-treat approach (i.e., all participants randomized will be included in analysis) within the

ANCOVA framework. The effects of interest are differences between experimental conditions at post-test and follow-up on youth, parent, and family outcomes, as detailed in the logic model (Research Strategy, Figure 1). These effects indicate whether the outcomes in the intervention condition differ significantly from those in the wait-list control condition. The experimental condition is the independent variable in these models. We will include pertinent covariates (e.g., pre-test measurement of outcome of interest, cohort, youth gender) in all models. At pre-test, we expect that the mean difference between the experimental conditions will not differ significantly from zero, reflecting effective randomization. At post-test and follow-up, we expect the difference between the experimental conditions to be significantly greater than zero, reflecting better outcomes after the intervention period for those in the Was'ake Tiwahe program condition. If nesting is of concern based on preliminary ICC analyses, we will implement the outcome analysis using the ANCOVA framework within a mixed model with random effects for both conditions. We will evaluate our hypotheses by examining significance (p), confidence intervals, and the standardized difference between groups (d).

Aim 2d. Structural equation modeling (MSEM) will be utilized via Mplus software to test whether the intermediary outcomes (child, caregiver, and family outcomes) at post-test are at least partial mediators of the effect of the program on the primary outcome of youth ACEs at follow-up and whether there are moderators of the effect of the program on youth ACEs. Evidence of mediation will be determined using the product of coefficients method using parametric bias-corrected bootstrapping with 1,000 resamples to calculate the confidence intervals (CI). To test for moderation for dichotomous variables (e.g., gender), we will estimate SEM multiple group models, first allowing estimation of the path coefficients to vary freely across groups, and then constraining paths to be equal when a structural path coefficient of interest was significant for one group and not the other group. We will conduct model comparisons using the chi-square ( $\chi^2$ ) difference test (i.e.,  $\chi^2$ , p < .05 indicating moderation). For continuous moderators, they will be operationalized as cross-product interactions with condition (all variables mean-centered). Significant interactions will be probed.  Models will be evaluated for overall model fit via  $\chi^2$  statistic, root mean square error of approximation (RMSEA  $\leq$  .08), the comparative fit index (CFI  $\leq$  .08), and the Tucker-Lewis Index (TFI  $\geq$  .90), as well as the significance and directionality of included path coefficients. Nesting will be accounted for, as needed.

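### Shared programme groups in the intervention arm are modelled only if an ICC check says so, and the SAP text supplied gives no trigger; the likely effect on error is modest and the remedy is cheap

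*SAP*

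**What the plan says.** Under Preliminary Analyses (Nesting), the SAP states that "individuals will be randomized to groups of families who will receive the intervention together". It places the nesting in the treatment group and plans ICCs "based on group assignment and facilitator in relation to outcomes". It then adds: "If needed, the role of group clustering will be accounted for in all analyses".

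Under Outcome Analyses, Aim 2c makes ANCOVA the default and adds: "If nesting is of concern based on preliminary ICC analyses, we will implement the outcome analysis using the ANCOVA framework within a mixed model". That model is to have "within a mixed model with random effects for both conditions". Aim 2d closes with "Nesting will be accounted for, as needed" and takes its mediation intervals from "parametric bias-corrected bootstrapping with 1,000 resamples to calculate the confidence intervals".

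So the statistic (ICC) and its levels (group, facilitator) are named. What would make nesting matter enough to switch models is not. Nor does the text supplied say which outcome, time point or reporter decides, or how facilitator enters the model. Other decisions in the SAP do have numeric rules: 0.05 SD for baseline adjustment, fit-index cut-offs, and p < .05 for moderation.

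**The concern.** Grouped delivery is a design feature of one arm, known before any data are collected. Whether the analysis respects it is left to a preliminary look at ICCs calculated on the outcomes. This raises two issues.

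- **Prespecification.** The choice between a plain and a cluster-aware ANCOVA stays open until outcome data have been seen, and the rule for choosing is not written down.
- **Weak screen.** With few groups, a modest ICC will usually not be flagged. The plain ANCOVA then understates the standard error of the treatment comparison. In Aim 2d, a parametric bootstrap draws from the fitted model, so an interval from a model without a group term leaves out group variance.

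**Working it through.** **Inputs from the documents.** The protocol's Recruitment and Retention Plan has 160 families per condition: "we anticipate that we will retain 75% of the sample at the 8-month follow-up for a final sample size of 120 families per condition". Check: 160 × 0.75 = 120, and 640 × 0.75 = 480 persons. Both figures reproduce.

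**Assumptions.** The text supplied gives no group size, number of groups, ICC, or alpha for the outcome tests. I took analysed groups of m = 6, 8, 10 or 12 (k = 120/m = 20, 15, 12 or 10 groups), a residual ICC ρ of 0.05 or 0.10, two-sided 5%, one score per family, total variance 1 in each arm, and unclustered controls.

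**Step 1: cost of leaving groups out.** The design effect in the intervention arm is DE = 1 + (m − 1)ρ. True SE over plain SE is √((1 + DE)/2). Type I error is about 2[1 − Φ(1.96·√(2/(1 + DE)))]. For m = 12 and ρ = 0.10, DE = 2.1, the SE ratio is 1.245, the effective critical value is 1.96 × √(2/3.1) = 1.574, and the error is 11.5%.

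**Step 2: power of the screen.** The one-way F test at 0.05 detects clustering with probability P(F > F₀.₉₅/θ), where θ = DE/(1 − ρ), on k − 1 and 120 − k df. For m = 10 and ρ = 0.05, θ = 1.45/0.95 = 1.526, F₀.₉₅(11, 108) = 1.878 and 1.878/1.526 = 1.231. Power is 0.276, so the screen misses in 72% of trials.

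**Step 3: the two-stage rule.** I simulated 300,000 null trials per cell (Monte Carlo error about 0.04 points). The plain analysis is a pooled t-test. The cluster-aware analysis uses (between-group mean square)/120 + (control variance)/120 with Satterthwaite df.

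| m (k) | ICC | Screen misses | Groups never modelled | p<.05 gate per outcome | Always modelled |
|---|---|---|---|---|---|
| 6 (20) | 0.05 | 79% | 6.5% | 5.7% | 5.1% |
| 6 (20) | 0.10 | 55% | 8.0% | 5.9% | 5.0% |
| 8 (15) | 0.05 | 75% | 7.1% | 6.0% | 5.1% |
| 8 (15) | 0.10 | 49% | 9.2% | 6.2% | 5.1% |
| 10 (12) | 0.05 | 72% | 7.7% | 6.1% | 5.1% |
| 10 (12) | 0.10 | 45% | 10.3% | 6.3% | 5.1% |
| 12 (10) | 0.05 | 70% | 8.3% | 6.4% | 5.1% |
| 12 (10) | 0.10 | 42% | 11.6% | 6.6% | 5.2% |

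**Step 4: other triggers the wording allows.**
- Switch when the ICC estimate exceeds 0.10: 5.7–7.0% at ICC 0.05 and 5.9–7.5% at ICC 0.10.
- Switch when the estimate exceeds 0: 4.4–5.0% at ICC 0.02 to 0.10, so no inflation.
- One global flag raised by p<.05 on any of 3 or 6 outcomes (outcome correlation 0.3 or 0.6; 60,000 trials per cell): 5.0–5.8%.

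**Step 5: cost of always modelling when the true ICC is 0.** Against plain ANCOVA, intervals are on average 1.1–2.7% wider with an unconstrained group variance. With the usual fit that truncates a negative variance at 0, they are 3.7–6.3% wider and Type I error falls to about 4.0–4.3%.

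**The case against.** Much of the case on the other side stands.

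- **The plan does not ignore clustering.** A reader might infer that it does. In fact a clustered analysis is planned, conditionally.
- **One switch is the better reading.** The Nesting paragraph ends by applying any adjustment to all analyses. That favours a single decision, under which error is at most 5.8%. The per-outcome figures need a gate that no passage describes.
- **The upper ends need large groups.** Groups of 8 to 12 enrolled families at 75% retention leave 6 to 9 analysed. Analysed groups of 10 and 12 imply about 13 and 16 enrolled. For groups of 6 to 8, the per-outcome gate peaks at about 6.1–6.2%. The SAP also plans maximum likelihood on all randomised cases, so 120 complete families per arm is a simplification.
- **Grouping is known; a non-zero ICC is not.** Randomising to groups removes composition as an expected source of correlation, though shared delivery remains. A within-arm ICC also does not reveal the between-arm effect, so a reader should not infer that the gate lets an analyst pick the favourable answer.
- **Aim 2d.** A reader might infer a large false-positive rate for the mediated effect. High figures arise only if nesting is assumed always ignored. Part of them also belongs to the bias-corrected bootstrap, which in simulation runs at about 6% even at ICC 0. I give no rate for Aim 2d.
- **Facilitator.** The documents give no facilitator numbers, so no error rate can be stated.
- **Treatment group versus both conditions.** This could be read as a contradiction. It is not shown to be one, because wait-list grouping is simply not described.
- **Text not supplied.** SAP text ahead of Statistical Design, the power section the protocol refers to, and the reference cited for the mixed model could define the trigger or the model.

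None of this supplies a trigger in the text available, or makes a weak screen preferable to modelling a known design feature.

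**Conclusion.** The point holds as one of prespecification and method choice, with low to moderate severity. On the text supplied, a known design feature is modelled only after an unspecified check that would usually miss an ICC of 0.05 and would miss 0.10 about half the time. Depending on the rule adopted, Type I error runs from no inflation, through 5.0–5.8% (global flag) and about 5.7–6.6% (p<.05 per outcome), to about 11.7% if groups are never modelled at ICC 0.10 with groups of 12. A reader cannot tell which applies. The figures rest on assumed group sizes, ICCs and alpha. The absence of a rule can be asserted only for the text supplied.

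**What to change.** **Aim 2c.** Delete the ICC gate. Prespecify a partially nested mixed ANCOVA that always includes a programme-group random effect in the intervention arm, with arm-specific residual variance and Satterthwaite or Kenward–Roger df. Report ICCs descriptively. Reconcile the treatment-group wording under Nesting with the random effects for both conditions under Aim 2c, by saying whether wait-list families are grouped before the comparison. State whether the group variance may go negative, since this sets the cost shown in Step 5.

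**Facilitator.** Before outcome data are seen, state whether any facilitator leads more than one group and, if so, how that level is handled.

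**Aim 2d.** Replace the as-needed clause with a statement that the same group clustering is always carried into the mediation model and its interval.

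**If a rule already exists** in text not supplied, Aims 2c and 2d should at least cross-refer to it.

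**Cost.** Aim 2c needs SAP wording and a standard mixed model, with the small loss of precision in Step 5 if there is no clustering. Aim 2d may need some new code for the interval.
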